10.3.1 Severity

Severity describes the intensity of an event, and will be assessed as:

Mild: The AE does not interfere in a significant manner with the subject's normal functioning level. It may be an annoyance.

Moderate: The AE produces some impairment of function but not hazardous to health. It is uncomfortable and/or an embarrassment.

Severe: The AE produces significant impairment of functioning or incapacitation and/or it is a hazard to the subject.

If an AE changes in severity, the worst severity should be reported.

10.3.2 Causality

Causality will be assessed as:

Probable: A clinical event, including laboratory test abnormality, with a reasonable time sequence to administration of the drug, unlikely to be attributed to concurrent disease or other drugs or chemicals, and which follows a clinically reasonable response on withdrawal (dechallenge). Rechallenge information is not required to fulfil this definition.

Possible: A clinical event, including laboratory test abnormality, with a reasonable time sequence to administration of the drug, but which could also be explained by concurrent disease or other drugs or chemicals. Information on drug withdrawal may be lacking or unclear.

Unlikely: A clinical event, including laboratory test abnormality, with a temporal relationship to drug administration which makes a causal relationship improbable, and in which other drugs, chemicals or underlying disease provide plausible explanations.

10.4 Follow-up of Subjects after Adverse Events

AEs that are serious or those that the investigator assesses as relevant to follow from a trial perspective will be followed until they are recovered, stabilized or recovered with sequelae. The date and outcome will be recorded on the AE form in the eCRF. Other ongoing AEs will not be followed within the trial after the date of the contact 2, telephone interview.

10.5 Abnormal Laboratory Values

The reporting of abnormalities as both laboratory findings and AEs should be avoided.

An asymptomatic abnormal laboratory finding should only be reported as an AE if it is clinically significant.

Clinically significant abnormal findings noted before treatment start at Visit 1 will be recorded on the medical history page in the eCRF. New or worsening clinically significant abnormal findings will be recorded on the AE page in the eCRF.

If an abnormal laboratory value is associated with clinical signs and symptoms, the sign/symptom should be reported as an AE and the associated laboratory result should be considered additional information.

10.6 Reporting of Serious Adverse Events

The Investigator is responsible for ensuring that all SAEs are reported to the Sponsor or the sponsor's designee immediately, by e-mail (preferred) or fax, but in any event no later than 24 hours of any site staff becoming aware of the event. Initial notification should be followed as soon as possible by detailed written reports. The initial and follow-up reports should identify subjects by unique code numbers assigned in the trial and not by the subjects' names, personal identification numbers, and/or addresses. The following information is **mandatory** for the initial report:

- Subject trial identification data (ID)
- Trial treatment
- Start date (time, if relevant) of the trial treatment
- Brief description of the event (diagnosis)
- Start date (time, if relevant) of the event
- Seriousness criteria
- Causality assessment

For reported deaths, the Investigator should supply the Sponsor with any additional requested information (e.g. autopsy reports and terminal medical reports).

SAE REPORTING CONTACT DETAILS

A+ Science AB

[name] Medical Director

E-mail: [contact] (preferred)

[contact]

[contact]

The Sponsor is responsible for informing the Competent Authorities, the European Medicines Agency (EMA) and Ethics Committees of any individual case reports of SAEs that are determined to be reportable by the sponsor (i.e. adverse events considered as serious, related and unexpected [SUSARs]). SUSARs will be distributed by the Sponsor's

pharmacovigilance team within 7/15 working days to the EMA (EudraVigilance) and concerned Competent Authorities and Ethics Committees, according to local regulations. The investigator will be notified of safety issues/SUSARs according to current legislation.

10.7 Precautions/Overdose

Risks associated with intake of oral contrast agents include dysphagia with aspiration and secondary pneumonia. Although patients with acute problems are excluded, a pre-emergency small bowel status might be aggravated to an established ileus by ingesting a large volume. Oral contrast agents should not be given to unconscious patients, to those with swallowing disorders, or an acute abdomen.

Known sensitivity or allergy to contrast agent ingredients are exclusion criteria in clinical studies. However, unknown sensitivities or allergies might cause reactions that may need to be medically treated.

Iodine may be absorbed and causes disturbance of functional test of the thyroid gland for weeks.

Intravenously administered iodine may cause allergic reaction of various severity from a mild rash to intensive care unit treatment. Routines for handling these cases are well known to the staff which is regularly trained in dealing with emergency cases. Equipment for emergency care treatment is available at the clinic and the clinic is located in close proximity to the hospital emergency care department.

11 DEMOGRAPHICS AND BASELINE CHARACTERISTICS

Demographics and Baseline Characteristics consist of those parameters that are assessed only at screening/baseline.

11.1.1 Subject Demography

Subject demography consists of:

- Date of birth,
- Height,
- Weight,
- Sex

The body weight will be measured with standard scales, and the subject will be asked about height, at Visit 1, CT-scan.

11.1.2 Medical History

For the documentation of the medical history, any previous and concomitant diseases within the last 2 years before screening will be documented in the eCRF.

The medical history will be obtained by asking the subject and by inspecting his/her medical records if available.

For statistical analysis, all previous and concomitant diseases will be coded with Medical Dictionary for Regulatory Activities (MedDRA), the version of which will be provided in the trial report.

12 TRIAL CONDUCT

Table 4 Schedule of Events

Visit/Contact	0 Screening ^{a)}	1 CT-scan	2 Telephone interview and early termination ^{b)}
Day	-28 to -1	0	1-2
Visit window			12-48 hours
Subject information	X	X	
In/exclusion criteria		X	
Informed consent		X	
Pregnancy test ^{c)}			
Randomisation		X	
Subject demographics (incl. height and weight)		X	
Concomitant treatment		X	X
Concomitant illnesses		X	
Medical history		X	
Blood sample (clinical chemistry) ^{d)}		X	
Adverse event(s)		X	X
Dispensing of contrast agent		X	
Administration of Iodine contrast		X	
CT Scan		X	
Evaluation of contrast difference		X	
Evaluation of extension and distension composite score		X	
Evaluation of diagnostic ability		X	
Evaluation of contrast agent degradation		X	
Subject assessment of taste, smell, consistency etc.		X	
Compliance		X	

- a) No formal screening will be performed in the trial. However, since only one visit to the clinic is planned in this trial, all subjects will receive information regarding the trial prior to the clinic visit. Subjects will thus have time to consider participation and prepare questions, if needed.
- b) Also in case a subject is withdrawn after intake of the contrast agent the Early Termination form should be completed.
- c) Urine pregnancy test of all fertile females
- d) Blood sample (2 mL) will include Na, K, Ca, P in serum and will be taken prior to intake of contrast agents and post CT-scan.

12.1 Procedures by Visit

Visits should occur within the time windows specified in the schedule of events, Table 4. All times should be recorded using the 24-hour clock (e.g., 23:20, not 11:20 pm).

12.1.1 Contact 0 (Screening, Day -28 to Day -1)

Contact 0 (Screening) will take place up to 28 days before Visit 1.

Subjects referred for abdominal- or thoraco-abdominal CT-examination will be invited by letter to participate in the study. Referral letters that informs them on day and time for the CT-examination are routinely sent out within 4 weeks prior to the examination. The invitation is added to the referral letter together with the full subject information about the trial. Subjects that are interested in participating in the trial will be asked to contact the investigator. If the subject has not contacted the clinic a week before the examination the investigator will contact the subject to confirm if the subject is willing to participate or not.

During the screening period, the Investigator will:

- Provide the subject with an invitational letter providing information about the trial
- Document subjects interest of participation in the trial by entering interested subjects to the screening log,
- Provide interested subjects with full subject information by sending out subject information leaflet,
- Answer any questions the subject might have regarding the trial

12.1.2 Visit 1 (CT-scan, Day 1)

Subjects still interested in participating in the trial will, upon arrival to the clinic at the day of CT examination, be fully informed about the trial by the investigator and given opportunity to ask questions. Eligible subjects will sign the consent to participate form prior to randomisation and any treatment related procedures.

During Visit 1 the Investigator will:

- Provide the subjects with full subject information and answer any question the subject might have
- Obtain informed consent
- Check in-/exclusion criteria
- Randomise the subject
- Record demography parameters
- Record concomitant medication and illness
- Record medical history
- Take blood sample (2 mL) before and after contrast agent administration
- Dispense the contrast agent
- Record the subject's assessment of taste, smell, consistency etc.
- Check and record compliance
- Note adverse events
- Perform the CT-scan including providing iodine contrast agent
- Assess efficacy

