8.2 Exclusion Criteria

Subjects will not be enrolled if they meet any of the following criteria:

1. IV administration of iodine is contraindicated
2. Clinical suspicion, according to medical record, of fistula formation and/or leakage
3. Having swallowing disorders preventing intake of the contrast agents
4. Referral indication of small bowel disease(s)
5. Known allergy to egg albumen
6. Known sensitivity to any of the components of the investigational product or comparators
7. Having known manifest thyrotoxicosis
8. Having known phenylketonuria
9. Having known Glucose-6-phosphatase deficiency
10. Has taken any medication, absorbed through the small bowel, less than four hours before intake of the investigational product or comparators
11. Being, in the opinion of the investigator, unlikely to comply with the clinical trial protocol
12. Previously randomised to participate in this trial
13. Participating in, or having participated in another, non-oncology clinical trial where the final trial treatment was given within the last 6 weeks
14. Participating in an oncology clinical trial where the final full (i.e. non-maintenance) trial treatment was given within the last 6 weeks

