8.5 Subject Identification and Randomisation

Subjects referred to CT examination of the abdomen will receive an invitation to the CT examination by letter. An advertisement letter informing about the trial will be included in this referral letter.

All referrals for abdominal CT are read and prioritized by the investigator/sub-investigator. Those subjects, irrespective from which medical clinic, who the radiologist think are possible candidates for the trial, will have the advertisement letter added to the referral letter sent home to them with date and time for their CT-examination.

An invitation log will be kept with names of those receiving the advertisement letter. Subjects will subsequently be contacted by and asked if they are interested in participation. Those interested will be sent the subject information leaflet.

All subjects receiving the patient information leaflet will receive a screening number consisting of S followed by three digits: S-XXX starting with S-101.

The Investigator will allocate the screening numbers in ascending order.

Enrolled subjects who drop out of the trial before randomisation will retain their screening number.

Randomisation will occur at the clinic on the day of examination when all screening procedures have been performed and eligibility for the trial confirmed. Each randomised subject will receive a unique randomisation number consisting of R followed by three digits: R-XXX starting with R-101. Randomisation numbers will be allocated in strict ascending order according to a randomisation list

Randomised subjects who terminate their trial participation for any reason, regardless of whether trial drug was taken or not, will retain their randomisation number.

Subjects will be randomised on a 1:1:1 basis to Lumentin® 44, diluted Omnipaque® or Movprep®. The randomisation will be in blocks and stratified by gender as the drinking capacity differs between males and females.

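### Medical history, concomitant illness and medication are listed for recording after the open allocation, and nothing requires them to be documented before the arm is known

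*Combined protocol and SAP*

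**What the plan says.** Section 12.1.2 lists 14 steps for Visit 1. After information and consent come "Check in-/exclusion criteria" (third) and "Randomise the subject" (fourth). Demography is fifth, "Record concomitant medication and illness" sixth and "Record medical history" seventh. The blood sample and dispensing follow. Both schedules of events (1.1 and Table 4) also show the randomisation row above these rows.

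Section 8.5 sets the rule for timing: "Randomisation will occur at the clinic on the day of examination when all screening procedures have been performed and eligibility for the trial confirmed". Footnote a to both schedules says that there is no formal screening, and Contact 0 (12.1.1) consists of giving information, logging interest and answering questions.

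The synopsis and section 7.1 require consent before randomisation and say that demography, history and medication are recorded and a blood sample is taken just before drinking. They do not place the recording before or after randomisation. Section 9.4 confirms that the trial is open label.

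**The concern.** In an open trial, anything elicited by interview after allocation can be coloured by knowledge of the arm. Two uses of the data make this matter here.

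The first is safety. Section 13.4.5 leaves out of the adverse event tables any event that began before intake and did not worsen. All other events are treatment-emergent, and the arms are compared by Fisher's exact test. The solicited complaints in 7.2.3 (stomach ache, burping, wind, nausea, fullness) are subjective, and patients referred for abdominal CT may already have some of them. A fuller history in one arm would move complaints out of that arm's treatment-emergent count; a thinner one would do the reverse.

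The second is who is analysed. A violation that emerges while medication or history is being recorded emerges when the arm is already known and the subject already counts as randomised. Found a few minutes earlier, it would simply have meant that the subject was not enrolled.

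**Working it through.** The point rests on order rather than on a figure, so the sections are set side by side first.

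**1. Is the order fixed anywhere else?** Section 12.1.2 is the only place that gives a step-by-step list, and it has randomisation at step 4, medication and illness at step 6, and history at step 7. Section 7.1 and the synopsis are silent on the relation to randomisation. Section 8.5 refers to completed screening procedures, but with no formal screening and an information-only Contact 0, history and medication are not clearly among them.

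**2. What does the eligibility check rest on?** Exclusion 10 reads: "Has taken any medication, absorbed through the small bowel, less than four hours before intake of the investigational product or comparators". That can be settled only on the day. Section 9.7 schedules the medication interview for Visit 1, covering the previous two weeks. The items it requires are name, route, start and stop dates, dosage and indication. A clock time is not among them, so the four-hour window cannot be verified from the required record. Exclusions 2 and 7 to 9 turn on medical history, and 13 and 14 on recent trial treatment. History comes from asking the subject, with medical records if available (11.1.2).

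**3. What happens to a violation found late?**
- Section 8.3 lists it as a reason for withdrawal.
- Section 13.1.2 makes it by default a major deviation, which removes the subject from the per protocol set. The classification is made case by case with the sponsor at a data review meeting.
- Section 13.1.3 limits the full analysis set to subjects who were correctly included, so the subject drops out there too.

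The per protocol analysis is primary and the full analysis set is the sensitivity analysis. Both lose the same subject, so comparing them would not reveal the loss.

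**4. Can the primary result be affected?** Section 13.4.1 specifies an unstratified Wilcoxon rank sum test with no covariates. Baseline data do not enter it. The only route is set membership.

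**5. Scale of that route.** Inputs from 13.6.1: difference 1.50, SD 2.00, 40 against 20 evaluable, two-sided 5%.

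Power = Φ(Δ / (σ√(1/n₁ + 1/n₂)) − 1.96)

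- 40 and 20: σ√(0.0750) = 0.548; 1.50/0.548 − 1.96 = 0.78; power 0.782. This reproduces the plan's 78%.
- 36 and 18 (10% short, not made up): σ√(0.0833) = 0.577; 1.50/0.577 − 1.96 = 0.64; power 0.738.

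The second line is an illustration, not an estimate. It assumes a shortfall equal to the whole 10% drop-out allowance of section 8.4. Enrolment continues until 80 are evaluable, so late failures first use up spare places: 88 − 80 = 8 under the synopsis and 16.5.1, or 93 − 80 = 13 under 8.4.

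**The case against.** The strongest reply is that the plan already protects eligibility. The criteria check stands directly before randomisation in the same list, and 8.5 requires confirmed eligibility. Recording is documentation and does not show that nobody asked earlier. The investigators have read the referrals (8.5), exclusion 2 is judged from the medical record, and exclusions 7 to 9 concern known conditions. This stands. A reader might infer that subjects are randomised first and checked later, or that 12.1.2 contradicts 8.5; the text supports neither. What remains is that the documented evidence for the check is listed after it.

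The list is also not declared a sequence and cannot be strictly one: "Take blood sample (2 mL) before and after contrast agent administration" is a single step placed before dispensing. That is fair, and it is a reason to state the order rather than leave it to be inferred.

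Exclusion 10 is tied to intake and so stays open until drinking, whatever the order. True, but asking before allocation would catch medication already taken.

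On safety, adverse event reporting is open in any case, a complaint that worsens still counts as treatment-emergent, and Appendix 3 asks every subject about the same five complaints in the same way. These points limit the bias. They do not remove the part that comes from the history itself, which is the part that can be avoided without blinding.

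A reader might extend the point to the pre-dose blood sample. The documents do not support that. It measures Na, K, Ca and P, which no eligibility criterion uses, and a laboratory value taken before intake is not readily shaped by knowledge of the arm. The rule "Clinically significant abnormal findings noted before treatment start at Visit 1 will be recorded on the medical history page in the eCRF" belongs to the section on laboratory values and says little about interview history.

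**Conclusion.** The concern holds in a limited form. As listed, history, illness and medication are taken with the arm known, and no section requires otherwise. This leaves an avoidable opening for bias in the adverse event comparison, in either direction. It also leaves a chance that a missed violation comes to light after allocation and removes the subject from both efficacy sets.

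The conclusion assumes that staff follow the list as written and that some violations can escape the initial check. It does not show that either harm will occur. A reader might want to attach a rate to late eligibility failures, but the documents give none, and spare places may absorb some or all of the losses. Nor do the documents support a claim that the primary test is biased through baseline imbalance, since no baseline variable enters it. The point should be corrected because the change is simple, not because a large effect has been shown.

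**What to change.** In 12.1.2, move the randomisation step to after demography, concomitant medication (with the time of the last oral dose), concomitant illness and medical history. In 7.1, 8.5 and both schedules, add a sentence saying that these items are documented in the source records before the allocation is revealed.

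Source documentation is enough. Making the eCRF release the randomisation number would not fit the present set-up: numbers are allocated in order from a list (8.5), source data may not be entered directly into the eCRF (15.4), and entry may take up to a week (15.6).

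No procedure is added. The cost is time on the day: foam preparation takes 30 minutes at room temperature plus 5 minutes of whipping (Appendix 1), and if it waits for the allocation it can no longer overlap with history-taking. It therefore starts slightly later.

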12.1.3 Contact 2, Telephone interview

The subject will be contacted by telephone by the investigator 12 to 48 hours after the CT-scan visit and interviewed about any possible adverse events that has occurred during the period after the CT-scan. The interview will include a set of predefined questions (see appendix XX) and also an open question, e.g. “have you experienced any untoward events or side effects since you left the clinic”. Concomitant medication and any change in concomitant medication will also be checked.

During telephone interview, the Investigator will:

- Check any occurrence or change in adverse events
- Check of use or change in concomitant medication

SAE and other AEs that the investigator assesses as relevant to follow from a trial perspective will be followed up, see section 10.4

13 STATISTICAL METHODS

Before disclosure of randomisation codes, a separate statistical analysis plan (SAP) may be finalised, providing detailed methods for the analyses outlined below.

In general, data summaries will be stratified by the randomised treatment group (Lumentin® 44, diluted Omnipaque® and Movprep®). The randomisation is stratified by gender and this will be taken into consideration in the statistical analyses

Any deviations from the planned analyses will be described and justified in the final integrated trial report.

13.1 Trial Subjects

13.1.1 Disposition of Subjects

The number and percentage of subjects will be presented, stratified by treatment and overall, with sub-stratification by randomisation stratification factors.

Reasons for withdrawal will also be summarised.

13.1.2 Protocol Deviations

Deviations to the trial protocol will be documented in a Protocol Deviation Log.

Deviations from the protocol including violations of inclusion/exclusion criteria will be assessed as “minor” or “major” on a case-by-case basis in cooperation with the Sponsor. This assessment will take place during a data review meeting. Major deviations from the protocol will lead to the exclusion of a subject from the per protocol analysis set.

Unless decided otherwise during the data review meeting, the following will be major protocol deviations:

- Deviations of inclusion/exclusion criteria,
- Subjects not able to drink at least 750 mL Lumentin® 44
- Subjects not able to drink at least the, according to the general praxis of care, recommended dose of diluted Omnipaque®
- Subjects not able to drink at least the, according to the general praxis of care, recommended dose of Movprep®

